Protocol Name:	Investigational Study of the Ekso Bionics Powered Exoskeleton for High-Dosage Use by Individuals with Spinal Cord Injury in a Non-Clinical Environment
	Principal Investigator:	[name], Sr. Controls Engineer
	Primary Contact Name/Contact Info:	[name], Sr. Controls Engineer [contact] [contact]
	Date Revised:	9/28/2015
	Study Number:	13098-01

Investigational Study of the Ekso Bionics Powered Exoskeleton for High-Dosage Use by Individuals with Spinal Cord Injury Walking in a Non-Clinical Environment

1. Investigator

Facility PI: [name], Sr. Controls Engineer, Ekso Bionics

2. Date Revised

September 28, 2015

3. Objectives

- 3.1 To determine the physiological effects of high-dosage use of the Ekso device over a 12- 36-month period.
- 3.2 To documents the quality of life benefits of using an Ekso device in a non-clinical setting.
- 3.3 To define the safety and efficacy of using the device in a home environment.
- 3.4 To determine the safety and efficacy of a non-medical professional spotting the subject.
- 3.5 To determine inclusion/exclusion criteria for an Ekso Bionics device used in a home setting.

4. Background

The incidence of spinal cord injury is estimated at 1.5-5.3 million worldwide.⁽¹⁾ "Will I walk again?" is often cited as one of the more common questions, with the decreased ability to walk as one of the most difficult challenges to live with.^(2,3) Over the last 10 years more research has focused on the ability for the spinal cord to "heal" itself, i.e. undergo plasticity,^(4,5) by task-specific, high-

	Protocol Name:	Investigational Study of the Ekso Bionics Powered Exoskeleton for High-Dosage Use by Individuals with Spinal Cord Injury in a Non-Clinical Environment
	Principal Investigator:	[name], Sr. Controls Engineer
	Primary Contact Name/Contact Info:	[name], Sr. Controls Engineer [contact] [contact]
	Date Revised:	9/28/2015
	Study Number:	13098-01

intensity activities.^(4, 6) Two major groups of task specific activities for ambulation have been developed. The first option is conventional over the ground training (CONT), where a number of therapists help support the subject while the others assist in moving the limbs in a reciprocal gait pattern. The other option, body weight supported training (BWST), involves partial support of the subjects weight via a harness while a therapists moves the lower limbs in a reciprocal gait pattern either over ground, in water or over a treadmill. A subset of BWST uses a robotic device in place of a therapist to move the limbs in a reciprocal gait pattern. The advantages of BWST include starting training before the subject can fully bear weight, prior to developing adequate motor control, and with greater safety and less fear of falling.⁽⁷⁾ The effort required of the therapists to assist and guide limb movement was the major challenge that resulted in development of robotic assisted devices.^(6, 8)

Overall a number of studies have reported improvements in various gait parameters including walking speed, amount of physical assistance needed, and the degree and type of assistive devices needed.^(7, 9, 10-13) Previously it was thought that CONT and BWST were equivalent in outcomes^(7, 14). More recent reviews suggest that BWST whether therapy assisted or robotically assisted does not produce greater return in walking independence or velocity of gait.^(11, 15) However the greatest benefit of CONT was seen among individuals with incomplete SCI while those with more severe impairments (i.e. complete motor paralysis) benefited from BWST⁽¹³⁾.

In addition to the potential for spinal cord plasticity and recovery of walking function, ambulation after SCI may also offer secondary health benefits. Kohout and colleagues⁽¹⁶⁾ reported that the ability to walk more than 1000 feet was related to a decreased need for pain and spasticity medications. Similarly, BWST has been associated with decreased spasticity of the plantar flexors and quadriceps muscles⁽¹⁷⁾. In contrast, Giannantoni and coworkers⁽¹⁸⁾

	Protocol Name:	Investigational Study of the Ekso Bionics Powered Exoskeleton for High-Dosage Use by Individuals with Spinal Cord Injury in a Non-Clinical Environment
	Principal Investigator:	[name], Sr. Controls Engineer
	Primary Contact Name/Contact Info:	[name], Sr. Controls Engineer [contact] [contact]
	Date Revised:	9/28/2015
	Study Number:	13098-01

found a worsening of urodynamic function following ambulation in a reciprocating-gait orthosis. A recent review on the physiological benefits of ambulation following SCI provided 2 conclusions from the literature: 1) the current evidence is controversial and mostly anecdotal; 2) physiological benefits of walking after SCI were most evident when ambulation was performed for at least 4-5 hours per week and over a long period of time ⁽¹⁹⁾.

[figure not shown]
Currently there is no cure for spinal cord injury ⁽²⁰⁾ however there have been improvements in therapies that promote a greater chance for neurological recovery. The evidence supporting gait training in spinal cord injuries suggests that starting early, utilizing task specific activities, and continuing the activities for long durations are beneficial. ⁽²⁰⁾ CONT training offers task specificity, however is labor intensive, time consuming, and requires a high degree of expertise to avoid injury. Moreover, those that are more severely impaired cannot begin CONT training early or safely offering a potential benefit of BWST in this subpopulation. BWST requires larger physical space for the treadmill can only be found at specialty centers and cannot be utilized at home. Therefore there is an opportunity to develop a "hybrid" of these 2 training paradigms. One that can allow for early participation despite severity of injury, can reduce the intensity of therapy assistance, can optimize the benefit of over ground training, and has the potential to be utilized in the home setting.

Recently the benefit of body weight supported training, either therapy assisted or robotically, has been questioned to be no greater than conventional over the ground training. ⁽²¹⁾ However, traditional training for those subjects with severe injuries is very labor intensive and difficult. Technology that blends the "labor reduction" benefit of BWST and the task specific benefit of over the ground training may provide the optimal solution. Therefore development of technologies that are easier to use, cheaper to implement and more

	Protocol Name:	Investigational Study of the Ekso Bionics Powered Exoskeleton for High-Dosage Use by Individuals with Spinal Cord Injury in a Non-Clinical Environment
	Principal Investigator:	[name], Sr. Controls Engineer
	Primary Contact Name/Contact Info:	[name], Sr. Controls Engineer [contact] [contact]
	Date Revised:	9/28/2015
	Study Number:	13098-01

readily accessible by the general spinal cord injured population is important.

One such device recently developed is the Ekso. The Ekso is an anthropomorphic mobile exoskeleton that is intended for rehabilitation and increased mobility for those suffering from muscular and neurological conditions affecting their lower extremity. The device is used to drive the subject's lower extremity joints through a desired trajectory in order to obtain a user specified motion. The device is mobile and holds all necessary batteries and processing on board for at least 2 hours of consistent use. The batteries are also interchangeable allowing for fully charged batteries to be swapped into the machine whenever required. The device is designed to adjust easily to fit a wide range of users. This adjustment is made using adjustments at the thigh and shank to adjust length and at the hips to adjust frontal plane width. The device is attached to the user's torso with backpack style shoulder harnessing and a torso brace. The other harnessing on the device are upper thigh straps, shin guards on the shank and secure foot binding.

The device is electrically powered by four electric motors at the user's knee and hip joints in the sagittal plane. The flexion and extension directions at the hip and knee are the only actuated degrees of freedom on the device. The device is equipped with mechanical hard stops at the limits of healthy subject ranges of motion to prevent powering the joint of the user to a position that the joint cannot reach. The actuated range of motion at the hip is -20° to 135° and the actuated range for the knee is 0° to 120°. Not all of this range of motion is needed in normal walking; however the ranges of these joints were selected to provide for other necessary functions such as standing and sitting. At the ankle the device is passive, with springs to resist sagittal plane motion and locked in the other degrees of freedom. The range of motion provided at the

Protocol Name:	Investigational Study of the Ekso Bionics Powered Exoskeleton for High-Dosage Use by Individuals with Spinal Cord Injury in a Non-Clinical Environment
Principal Investigator:	[name], Sr. Controls Engineer
Primary Contact Name/Contact Info:	[name], Sr. Controls Engineer [contact] [contact]
Date Revised:	9/28/2015
Study Number:	13098-01

ankle is from -10° to 20° dorsiflexion with hard stops at the limits of this range to protect the user. The final degree of freedom is a manual lock for abduction at the hip. When released, the device is free to swing in the abduction direction (used for donning/doffing purposes) but when locked the device prevents motion in both the abduction and adduction directions.

The device operates using a number of important sensors. There are foot pressure sensors at the heel and toe of both feet to determine the forces between the user and the ground at those locations. Multiple position sensors determine the angle of each actuated joint. A body tilt sensor is used to find the lean of the torso in space. Finally, temperature sensors are used to monitor the motor and drive temperatures.

The control code in the device operates by creating an internal estimate of the subject's current position and then coordinating the motion of the four actuated degrees of freedom to take the desired motion. The desired motion is specified through an attached user interface that can be controlled by the user or a therapist. The device can stand from a seated position, walk and sit down. In actual operation the device is triggered by various modes. The first mode is used early in training where the therapist manually triggers the steps with the user interface. For advanced users the machine can operate in a different mode and interpret their posture to determine when steps are desired.

The Ekso provides full weight bearing, over ground reciprocal gait training. The robotic exoskeleton reduces the need for therapy guidance and can free the therapists up for safety spotting and feedback, ultimately reducing the number of therapists required. In addition the low profile allows for use in varied environments both indoor and outdoor, and the size of the device can potentially allow for ease of transport for use at home. As such subjects can continue to utilize the principle of "start early" as the robotic components

	Protocol Name:	Investigational Study of the Ekso Bionics Powered Exoskeleton for High-Dosage Use by Individuals with Spinal Cord Injury in a Non-Clinical Environment
	Principal Investigator:	[name], Sr. Controls Engineer
	Primary Contact Name/Contact Info:	[name], Sr. Controls Engineer [contact] [contact]
	Date Revised:	9/28/2015
	Study Number:	13098-01

allow for utilization of more severely injured subjects; "task-specific" as the robotic limb trajectory mirrors a normal gait pattern, and "keep it going" as the ability to use the device out of the classic rehabilitation setting will allow for greater duration of use.

It is anticipated that modifications to the hardware and software will be developed and implemented throughout the testing of the device as required to better meet the needs of subjects. Some of these modifications that already exist include a sagittal plane actuated ankle, a passive hip frontal plane degree of freedom, a passive hip rotation degree of freedom, and a leg with reduced actuation for higher functioning subjects. Each of these modifications maintains the current safety features included in the existing manufactured device. These safety features include mechanical hardstops to limit the range of motion to less than a non-disabled person's range of motion, redundant position sensing at all actuated joints, monitoring of sensors to identify device failures prior to injury, and padding at all points where the subject and device make contact. All future device modifications will hold to these design safety features.

5. Fawcett JW, Curt A, Steeves JD. Guidelines for the conduct of clinical trials for spinal cord injury as developed by the ICCP panel: spontaneous recovery

Protocol Name:	Investigational Study of the Ekso Bionics Powered Exoskeleton for High-Dosage Use by Individuals with Spinal Cord Injury in a Non-Clinical Environment
Principal Investigator:	[name], Sr. Controls Engineer
Primary Contact Name/Contact Info:	[name], Sr. Controls Engineer [contact] [contact]
Date Revised:	9/28/2015
Study Number:	13098-01

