This is a 36 month exploratory Investigational Study compliant with the NSF Human Subjects regulations (45 CFR 690) trialing a new device for the SCI populations to aid in ambulatory function in a home setting. Ekso Bionics will enable up to twelve (12) subjects with SCI to use an Ekso device in their home for a 12-month period. Qualified subjects will help Ekso Bionics determine the practical use of the device in the home environment and will enable Ekso Bionics to gather data to develop a device for use in a home environment. The study will require a trained spotter to be present at all times that the device is being used. The study will also evaluate the effectiveness of a non-medically licensed spotter to assist the subject.

6.1. The study will measure and evaluate the following to enable Ekso Bionics to determine the physiological benefits of high-dosage use of the device in the home. Baseline measures will be recorded at the beginning of the study and reassessed a minimum of every three months over a twelve month period (+/- 2 weeks) and every 6 months after (+/- 2 weeks). The metrics include:

- 6.1.1. The number of Ekso sessions completed
- 6.1.2. Number of steps taken in device (per week, average per session, whole time)
- 6.1.3. Time spent walking in device (per week, average per session, whole time)

	Protocol Name:	Investigational Study of the Ekso Bionics Powered Exoskeleton for High-Dosage Use by Individuals with Spinal Cord Injury in a Non-Clinical Environment
	Principal Investigator:	[name], Sr. Controls Engineer
	Primary Contact Name/Contact Info:	[name], Sr. Controls Engineer [contact] [contact]
	Date Revised:	9/28/2015
	Study Number:	13098-01

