6.1.4. Duration of training session in each walking mode (FirstStep, ActiveStep, ProStep)

6.1.5. Perceived rate of exertion (PRE) - Borg Perceived Rate of Exertion Scale

6.1.6. Bowel function - Modified International SCI Bowel Function Basic Data Set

6.1.7. Bladder function - Modified International SCI Lower Urinary Tract Basic Data Set

6.1.8. Frequency of secondary health conditions (urinary tract infections, pressure ulcerations, respiratory conditions)

6.1.9. Quality of life (QOL) - International SCI Quality of Life Basic Data Set

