6.1.14. Bone Density - DEXA Scan (Initial and 12 month)

6.2. The subject will identify an individual to spot them for safety during every moment of device use. The individual may be a relative, friend or an individual hired by the subject. The spotter will not likely be a medical professional although Ekso Bionics will consider a medical profession as a spotter. The spotter must meet the Inclusion/Exclusion criteria listed below. Ekso Bionics clinicians will train the spotter with the subject in the device over a three day period in the subject's home environment (Appendix A). The spotter must be certified as

	Protocol Name:	Investigational Study of the Ekso Bionics Powered Exoskeleton for High-Dosage Use by Individuals with Spinal Cord Injury in a Non-Clinical Environment
	Principal Investigator:	[name], Sr. Controls Engineer
	Primary Contact Name/Contact Info:	[name], Sr. Controls Engineer [contact] [contact]
	Date Revised:	9/28/2015
	Study Number:	13098-01

competent by Ekso Bionics' clinicians in order for the device to be used without an Ekso Bionics clinician present. If the spotter is not approved, the subject may locate another spotter. Due to the time commitment required of the spotter, each subject may choose to train up to two spotters during the initial spotter training sessions.

6.3. Subject training will include but is not limited to:

- 6.3.1. Informing of device functions, failure modes and common characteristics.
- 6.3.2. Safety and how to respond to various conditions including being off balance, uneven surfaces.
- 6.3.3. Device set-up and take-down
- 6.3.4. Operating the device.
- 6.3.5. Putting the device on and taking the device off.
- 6.3.6. Sitting/Standing
- 6.3.7. Walking
- 6.3.8. Balance
- 6.3.9. Using hands when in the device

6.4. Spotter training will include but is not limited to:

- 6.4.1. Informing of device functions, failure modes and common characteristics.
- 6.4.2. Safety and how to respond to various conditions including being off balance, uneven ground.
- 6.4.3. Device set-up and take-down
- 6.4.4. Operating the device.
- 6.4.5. Putting the device on and taking the device off.
- 6.4.6. Sitting/Standing
- 6.4.7. Walking
- 6.4.8. Supporting the subject

Protocol Name:	Investigational Study of the Ekso Bionics Powered Exoskeleton for High-Dosage Use by Individuals with Spinal Cord Injury in a Non-Clinical Environment
Principal Investigator:	[name], Sr. Controls Engineer

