Primary Contact Name/Contact Info:	[name], Sr. Controls Engineer [contact] [contact]
Date Revised:	9/28/2015
Study Number:	13098-01

6.4.9. Helping the subject safely perform simple daily tasks inaccessible to the subject while in the device (e.g., bend down to get a plate from a cabinet or open a door)

6.5. Ekso Bionics will:

6.5.1. Evaluate the efficacy of a spotter in a home environment.
6.5.2. Evaluate the safety of using the device in a home environment.

6.6. After initial training at either Ekso Bionics or at the participant's home, a follow-up evaluation device operation may be conducted either in-person or by video at weeks 3 and 7. Review meetings will be held every three months from the time the device is delivered to the subject's home (or more frequently) to evaluate safety and efficacy. Information gathered from the study and status meetings will be used by Ekso Bionics to further the product development. Information may also be used by Ekso Bionics Marketing to determine the most appropriate market for the device and by Clinicians to aid in training future clinical staff.

Schedule of study measure.

	Baseline	3 months	6 months	9 months	12 months	Every 6 months after
Device measures (6.1.1 – 6.1.4)		✓	✓	✓	✓	✓
Physiological measures (6.1.5 – 6.1.7)	✓	✓	✓	✓	✓	✓
Frequency of secondary health conditions (6.1.8)	✓	✓	✓	✓	✓	✓

	Protocol Name:	Investigational Study of the Ekso Bionics Powered Exoskeleton for High-Dosage Use by Individuals with Spinal Cord Injury in a Non-Clinical Environment				
	Principal Investigator:	[name], Sr. Controls Engineer				
	Primary Contact Name/Contact Info:	[name], Sr. Controls Engineer [contact] [contact]				
	Date Revised:	9/28/2015				
	Study Number:	13098-01				

Quality of Life measures (6.1.9)	√	√	√	√	√	√
Functional ability (6.1.10)	√	√	√	√	√	√
Pain (6.1.11)	√	√	√	√	√	√
Spasticity (6.1.12)	√	√	√	√	√	√
Strength testing (6.1.13)	√	√	√	√	√	√
Bone Density (6.1.14)	√				√	

7. Inclusion and Exclusion Criteria

7.1. Subject Inclusion Criteria:

Participants must have a spinal cord injury between C7-L3 resulting in motor paralysis.

Participants must meet each of the remaining criteria:

7.1.1. be an experienced user of the Ekso device with a minimum of 20 hours and no more than 50 hours of device use and require no greater than minimal assist (support of up to 25% body weight) for safe and consistent walking.

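### Safety of home use and of a lay spotter is an objective, but no listed measure counts untreated falls, caught balance losses or spotter injuries when they happen

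*Protocol*

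**What the plan says.** Two of the five objectives concern safety in the setting studied. Objective 3.3 is "To define the safety and efficacy of using the device in a home environment" and objective 3.4 is "To determine the safety and efficacy of a non-medical professional spotting the subject". Section 6.5.2 repeats the home-use part ("Evaluate the safety of using the device in a home environment"), while 6.5.1 names the efficacy of the spotter only. Under 6.2, a spotter must be certified "in order for the device to be used without an Ekso Bionics clinician present", so unsupervised use with a lay spotter is a planned condition of the study.

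The 14 measures of section 6.1 are introduced as a means "to determine the physiological benefits of high-dosage use of the device in the home". Among them, the only item that counts medical events is 6.1.8, "Frequency of secondary health conditions (urinary tract infections, pressure ulcerations, respiratory conditions"). The list also supplies a denominator, 6.1.1: "The number of Ekso sessions completed".

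The daily log (12.2.8), kept by both subject and spotter, lists five items: sleep, departures from usual daily activity, other physical activity, a quality-of-life rating and general impressions. Section 16 discusses falling (16.1) and musculoskeletal injury of the spotter, including when lifting or moving the device (16.8), as risks to be mitigated. Section 7.1.1.1 sets a limit on balance losses per session by level of assistance, as an entry criterion.

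**The concern.** A safety objective needs a record of the events that would show the arrangement to be unsafe. For a lay spotter working without a clinician, the most informative events are falls, losses of balance that the spotter had to catch, and injuries to the spotter. The protocol recognises all three, but lists none of them as something to be recorded during home use.

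This cannot be left to an analysis plan. An analysis plan decides how to summarise what was captured. A minor event in a private home that nobody was asked to note is lost. At the end of the study, an absence of reports could mean that nothing happened or that nothing was asked, and objectives 3.3 and 3.4 would be unanswered for these events.

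**Working it through.** The protocol states no event rate, sample-size calculation or safety figure to reproduce. The check is therefore a comparison of sections, followed by one illustration.

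**Where could the events be recorded?**

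- *6.1.1 to 6.1.14 and the schedule table:* use, exertion, bowel, bladder, three secondary conditions, quality of life, function, pain, spasticity, strength and bone density. There is no row for falls, balance losses or spotter injury. Pressure ulcerations (6.1.8) and within-session pain (6.1.11) are safety-related but are different events.
- *Daily log, 12.2.8.1 to 12.2.8.5:* none of the five listed items asks about these events. The items on departures from usual activity and on general impressions might attract a mention, but do not prompt for one.
- *On-board data, 12.2.2 to 12.2.7 and 14.3:* steps, step length, speed, mode, battery, distance, forces and position. Both lists are open-ended, so faults and shutdowns may be there. A spotter hurt while lifting the device would not be.
- *Sponsor observation, 12.3.4 and 12.3.7:* balance and stability, and device reliability, but as observed by the sponsor and without a defined count.
- *Periodic contact:* clinician evaluations against the entry criteria (12.2.1), possible evaluations at weeks 3 and 7 and three-monthly reviews whose stated purpose includes safety (6.6), and the 12-month interview or questionnaire (11.1). For minor events between contacts these depend on recall.
- *Video, 14.1 and 14.8:* a possible source and a means of verifying data. Continuous recording of home use is not stated.
- *Harm reporting, 17.1:* applies when medical resources are needed.

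No visible item is a count, made at the time by subject and spotter, of untreated falls, caught balance losses or spotter injuries.

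**What could a count support?** This is an illustration only, because 12.2.9 leaves the amount of use to the participant.

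Inputs: 2 to 12 subjects (section 9); at least 12 months each (section 10); spotter availability of at least 4 days a week in 5 of every 6 weeks (7.3.7). Assumption: one session per covered day.

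- Sessions per participant-year: 4 × 52 × 5/6 = 173.3.
- Total sessions: 12 × 173.3 = 2,080; 2 × 173.3 = 347.
- Two-sided 95% upper limit after zero events: −ln(0.025)/sessions = 3.689/sessions.
- With 12 subjects: 3.689/2,080 = 1.8 per 1,000 sessions.
- With 2 subjects: 3.689/346.7 = 10.6 per 1,000 sessions.

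At an assumed one session a week, the totals are 12 × 52 = 624 and 2 × 52 = 104 sessions, and the limits are 5.9 and 35.5 per 1,000. All four limits assume no clustering of events within a participant, so they are the favourable case. They can be quoted only if zero is a recorded zero.

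**The case against.** The strongest reply is that the recording instruments are not visible. The daily log (Appendix D) and the spotter questionnaire (Appendix C) are shown by title only, and the five listed log items need not be the whole form: exertion (6.1.5) and within-session pain (6.1.11) must be recorded somewhere and are not among the five. This stands. It limits the point to what the protocol lists, and it may reduce the remedy to a cross-reference.

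A second reply is that safety is not ignored. The 6.6 reviews are planned safety assessments, 12.3 covers balance and device reliability, and 17.1 deals with events needing care. This also stands. A reader might infer that the protocol collects no safety data, or that serious injuries would go unnoticed; the documents do not support either. Nor do they support a claim that device faults and emergency stops go unrecorded, since the on-board data lists are open-ended. What the reply does not supply is a contemporaneous count of minor events when no clinician is present.

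Third, objective 3.4 can be read as concerning the subject's safety only, so that spotter injury is not a stated endpoint. That reading is possible. Section 16.8 nevertheless treats spotter injury as a risk of the study, and falls and caught balance losses remain under either reading.

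**Conclusion.** The point holds in a limited form. For falls without medical care, caught balance losses and spotter injuries during use with the spotter alone, the listed measures give no contemporaneous count, so those parts of objectives 3.3 and 3.4 could not be answered from them. This should be corrected. Confidence is medium, because the Appendix C and D forms are not shown.

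The frequency of these events is unknown. It is tempting to multiply the balance-loss limit in 7.1.1.1 by an assumed number of sessions to estimate how many events would be missed. The documents do not support that: the limit is an entry ceiling and not a rate, 7.3.7 describes spotter availability and not use, and use is discretionary. The zero-event limits above are likewise conditional on the session assumptions. They show what a recorded zero would be worth, and the finding does not depend on them.

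**What to change.** Add fields to the daily log, to be completed by both subject and spotter, and list them in 6.1 and the schedule table as the measures for objectives 3.3 and 3.4:

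- falls, whether or not medical care was needed;
- balance losses, by the assistance grades of 7.1.1.1;
- spotter injury, including when lifting or moving the device;
- an explicit 'none' box, so that a blank is not read as zero.

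Take device faults and emergency stops from the on-board data, and name them among the items in 12.2. Report counts by participant, with sessions (6.1.1) as the denominator. Walking time (6.1.3) would not suit injuries that occur outside walking.

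The cost is a few tick boxes on an existing form, slightly more daily burden for two people, and one descriptive table. Intervals will stay wide with 2 to 12 subjects. If the Appendix C or D forms already hold these fields, it is enough to list them in 6.1 and the schedule.
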